7.0 STATISTICAL ANALYSIS PLAN

7.1 Statistical Analysis Plan Summary

For this exploratory pilot study, sample size was calculated based on a hypothesis of anticipated clinical efficacy and compared with historical clinical trial data. As this is a single arm study, no formal statistical comparisons will be made.

7.2 Statistical Analysis Plan

This represents a single-arm signal finding pilot study. As such, no formal statistical comparisons will be conducted. However, using historical data from prospective clinical trials and retrospective case series reported in the literature, therapy with PD-1 inhibitors results in objective response rates of approximately 10% and median progression free survival of approximately 3.5 months (reviewed by Wessely A., et al. International Journal of Molecular Sciences 2020) [27].

In this 30 patient pilot study, using a one-sided test with a type I error of 0.05, the power for detecting a difference in the ORR compared with the historical average of 10% ORR with anti-PD-1 monotherapy varies with the hypothetical experimental ORR as follows:

Hypothetical experimental ORR	Historical average ORR	Power
20%	10%	0.55
25%	10%	0.78
30%	10%	0.91

Interim futility analysis/stopping rules: After 15 evaluable subjects have been enrolled and treated (defined as having received scheduled treatment per protocol for at least 1 cycle and have completed restaging imaging) - an interim futility analysis will be conducted. If the objective response rate is less than 20% (3 of 15 subjects) or the median progression free survival is less than 6 months - enrollment will stop.

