Tumor Imaging (chest, abdomen, & pelvis) and iRECIST Assessment Note: Imaging of the brain required only at screening.		Х							X		Х	X	X		X		Imaging is performed at Screening, Week 9 and every 9 weeks (± 7 days) during Year 1. After Year 1, imaging is performed every 12 weeks (±7 days). This schedule will be maintained regardless of treatment delays.

Confidential

Study Period:	Scre	ening			Ι	nterve	ention	(21-D	ay Cy	cles)				Post	treatment Vis	sits	Notes
Visit Number/Title:	1/Scro	eening	1	C1	15	(22	C3	C4	C5	C6 to C35	\geq C36	End of Treatment	Safety Follow-	Efficacy Follow-	Survival	
Scheduling Window (days)	-42 to - 1	-28 to - 1	±3	8 ±3	±3	±3	±3	±3	±3	±3	±3	±3	At time of treatment discontin uation	Approx. 30d after last dose (± 7d)	up Q6W (Y1) or Q9W (Y2+) (± 7d)	Q12W ^a (± 14d)	
Safety Procedures	1	1	r –	1	r	r –	r	r –	r –	1		r	1	1	1	Γ	
AE/SAE Review	x	x	x	x	x	x	x	x	x	x	x	x	x	х	х		Report AEs occurring within 30 days after the last dose of study intervention. Report SAEs occurring within 90 days after the last dose of study intervention, or 30 days after the last dose of study intervention if a new anticancer therapy is initiated, whichever is first.
Full Physical Examination		Х											X				
Height		Х															
Directed Physical Examination			X		Х	X	Х	X	X	Х	Х	Х		Х			
Contact				x													The investigator or medically qualified designee (consistent with local requirements) will assess participants for development of early toxicity. An unscheduled visit can occur before C1D15 if necessary for safety.

Study Period	Scre	ening			I	nterve	ntion	(21-D	av Cv	cles)				Post tr	eatment Visi	its	Notes
Study Ferrou.	Sere	creening In					ntion				C6		_End of	1 050 0			10005
Vigit Number/Title:	1/50%	onina		C1		0	r'n	C2	C4	C5	to	\geq	Treatment	Safety	Efficacy	Second and	
Cvcle Dav	1/501	Jenning	1	8	15	1	15	1	1	1	1	1		Follow-	Follow-	FU	
Scheduling Window (days)	-42 to - 1	-28 to - 1	±3	±3	±3	±3	±3	±3	±3	±3	±3	±3	At time of treatment discontin uation	Approx. 30d after last dose (± 7d)	Q6W (Y1) or Q9W (Y2+) (± 7d)	Q12W ^a (± 14d)	
Vital Signs (resting BP, heart rate, RR, and temp) and weight		х	x		x	x	х	х	x	х	Х	Х	X	х			The Day 15 visit is mandatory for C1 and C2. During C3 and subsequent cycles, participants may return for the D15 visit if BP monitoring is required.

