3.0 OBJECTIVE(S), HYPOTHESIS(ES), AND ENDPOINT(S)

3.1 **Primary Objective(s), Hypothesis(es), and Endpoint(s)**

(1) **Objective:** To evaluate the effect of lenvatinib + pembrolizumab on progression free survival.

Hypothesis: Treatment with Lenvatinib + pembrolizumab will result in improved progression free survival as compared with previously reported systemic therapies including pembrolizumab monotherapy, ipilimumab + nivolumab and tebentafusp.

Primary Endpoint: Progression free survival, defined as the time from enrollment to the first documented evidence of disease progression or death.

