6.1.4 Tumor Imaging and Assessment of Disease

Tumor imaging is strongly preferred to be acquired by computed tomography (CT). For the abdomen and pelvis, contrast-enhanced magnetic resonance imaging (MRI) may be used when CT with iodinated contrast is contraindicated, or when local practice mandates it. MRI is the strongly preferred modality for imaging the brain. The same imaging technique regarding modality, ideally the same scanner, and the use of contrast should be used in a participant throughout the study to optimize the reproducibility of the assessment of existing and new tumor burden and improve the accuracy of the assessment of response or progression based on imaging.

Brain imaging is required for all participants at screening. MRI is preferred; however, CT imaging will be acceptable, if MRI is medically contraindicated. Participant eligibility will be determined using local assessment (Investigator assessment) based on RECIST 1.1. In addition, images (including via other modalities) that are obtained at an unscheduled time point to determine disease progression, as well as imaging obtained for other reasons, but which demonstrate radiologic progression, should also be used to determine progression.

When the Investigator identifies radiographic progression per RECIST 1.1, efforts should be made to verify radiologic PD. Treatment should continue until PD has been verified. Regardless of whether PD is verified, if the Investigator considers the participant has progressed, but elects to implement iRECIST, the Investigator will assess for confirmation of progression by iRECIST at subsequent time points.

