6.1.4.2 Tumor Imaging During the Study

The first on-study imaging assessment should be performed at 9 weeks (\pm 7 days) from the date of allocation. Subsequent tumor imaging should be performed every 9 weeks (\pm 7 days) or more frequently if clinically indicated. After 1 year (\pm 7 days), participants who remain on treatment will have imaging performed every 12 weeks (\pm 7 days). Imaging timing should follow calendar days and should not be adjusted for delays in cycle starts. Imaging should continue to be performed until disease progression is identified by the Investigator.

Objective response should be confirmed by a repeat imaging assessment. Tumor imaging to confirm PR or CR should be performed at least 4 weeks after the first indication of a response is observed. Participants will then return to regular scheduled imaging every 9 weeks, starting with the next scheduled imaging time point. Participants who receive additional imaging for confirmation do not need to undergo the next scheduled tumor imaging if it is less than 4 weeks later; tumor imaging may resume at the subsequent scheduled imaging time point.

Confidential

Per iRECIST (Section 6.1.4.6), disease progression should be confirmed by the site 4 to 8 weeks after first radiologic evidence of PD in clinically stable participants. Participants who have unconfirmed disease progression may continue on treatment at the discretion of the investigator until progression is confirmed by the site provided they have met the conditions detailed in Section 6.1.4.6. Participants who receive confirmatory imaging do not need to undergo the next scheduled tumor imaging if it is less than 4 weeks later; tumor imaging may resume at the subsequent scheduled imaging time point, if clinically stable. Participants who have confirmed disease progression by iRECIST, as assessed by the site, will discontinue study treatment. Exceptions are detailed in Section 6.1.4.5.

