6.1.4.3 End of Treatment and Follow-up Tumor Imaging

In participants who discontinue study treatment, tumor imaging should be performed at the time of treatment discontinuation (\pm 4 week window). If previous imaging was obtained within 4 weeks prior to the date of discontinuation, then imaging at treatment discontinuation is not mandatory. In participants who discontinue study treatment due to documented disease progression and the investigator elects not to implement iRECIST, this is the final required tumor imaging.

For participants who discontinue study treatment without documented disease progression, every effort should be made to continue monitoring their disease status by tumor imaging using the same imaging schedule used while on treatment (every 9 weeks in Year 1 or every 12 weeks after Year 1) to monitor disease status until the start of a new anticancer treatment, disease progression, pregnancy, death, withdrawal of consent, or the end of the study, whichever occurs first.

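### The interim futility look leaves out treated failures who never had a restaging scan, which tilts it modestly towards continuing (minor)

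*Combined protocol and SAP*

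**What the plan says.** Section 7.2 plans one interim futility look after 15 evaluable subjects. Enrollment stops "If the objective response rate is less than 20% (3 of 15 subjects) or the median progression free survival is less than 6 months". An evaluable subject is "defined as having received scheduled treatment per protocol for at least 1 cycle and have completed restaging imaging". No operating characteristics are given for this rule, and no analysis set, estimator or censoring rule is named for the interim median.

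These sections bear on how the rule works:

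- Section 3.1 defines the primary endpoint: "Progression free survival, defined as the time from enrollment to the first documented evidence of disease progression or death". Death is therefore a PFS event whether or not a scan was done.
- Section 2.3: "Imaging is performed at Screening, Week 9 and every 9 weeks" in Year 1. Section 6.1.4.2 agrees: "Subsequent tumor imaging should be performed every 9 weeks", with a window of 7 days either way.
- Section 6.1.4 lets "images (including via other modalities) that are obtained at an unscheduled time point to determine disease progression" count towards progression. Section 6.1.4.3 says "tumor imaging should be performed at the time of treatment discontinuation".
- Section 6.1.4.2: "Objective response should be confirmed by a repeat imaging assessment", at least 4 weeks after the response is first seen.
- For subjects who stop treatment without progression, Section 6.1.4.3 keeps 9-weekly imaging in Year 1, while Section 6.1.7.3.2 sets 6-weekly imaging.

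**The concern.** This is the plan's only prespecified stop for lack of activity; Section 5.6 covers data quality, adherence, safety and drug development. The definition of evaluable acts as a filter applied after treatment starts. Subjects who never reach a scan are mostly those who died or deteriorated early, and removing them raises the observed response rate. If the filter also governs the PFS limb, it lengthens the observed median as well. A reader who takes the 15 to be the first 15 treated would expect a stricter rule.

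The second question is whether a 6-month bar means what it appears to mean when progression is normally dated at scans 9 weeks apart.

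**Working it through.** **Inputs.** From Section 7.2: 15 subjects; stop at 0-2 responders or at a median below 6 months; historical ORR about 10% and median PFS about 3.5 months; 30 patients. From Section 1.0: 20 months of enrollment, so 30/20 = 1.5 per month. From Sections 2.3 and 6.1.4.2: scans at weeks 9, 18 and 27. Assumed: exponential PFS, independence of the two limbs, and 5% or 10% of treated subjects being unscanned failures.

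**The plan's own figure.** The power table in Section 7.2 reproduces with the one-sided normal approximation, power = Φ[(√30 (p₁ − 0.10) − 1.645 √(0.10 × 0.90)) / √(p₁(1 − p₁))]. It gives 0.55, 0.78 and 0.91 at 20%, 25% and 30%, as stated. The table concerns the final 30 subjects. There is no stated figure for the interim rule to reproduce.

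**Response limb, all treated.** P(stop) = P(X ≤ 2), X ~ Bin(15, 0.10), = 0.816. P(continue) = 0.184.

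**Response limb, filtered.** If a share f of treated subjects are unscanned failures, the ORR among those who count is 0.10/(1 − f).

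| f | ORR among evaluable | P(at least 3 of 15) |
|---|---|---|
| 0 | 0.100 | 0.184 |
| 5% | 0.105 | 0.205 |
| 10% | 0.111 | 0.228 |

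**Scan grid.** With 30.44 days to the month, weeks 9, 18 and 27 are 2.07, 4.14 and 6.21 months. Progression between weeks 18 and 27 is normally dated at week 27 and so counts as at least 6 months. Only the early edge of the window (week 26, 5.98 months) falls below. With every event on the grid and full follow-up, a median below 6 months means at least 8 of 15 failed by week 18. With p = 1 − 2^(−t/median):

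| Underlying median (months) | p by week 18 | P(≥8 of 15), on grid | P(≥8 of 15) by 6.0 months, exact dates |
|---|---|---|---|
| 3.5 | 0.559 | 0.68 | 0.95 |
| 6 | 0.380 | 0.17 | 0.50 |
| 8 | 0.301 | 0.05 | 0.23 |

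The exact-date column is illustrative only, because scheduled imaging cannot observe it.

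**Either limb.** P(stop) = 1 − P(≥3 responders) × [1 − P(PFS stop)].

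- ORR 10%, median 3.5 months. Exact: 1 − 0.184 × 0.055 = 0.990. Grid: 1 − 0.184 × 0.319 = 0.941.
- ORR 20%, median 6 months, where P(≥3 of 15) = 0.602. Exact: 1 − 0.602 × 0.500 = 0.70. Grid: 1 − 0.602 × 0.831 = 0.50.

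**Censoring rule.** The look was also simulated at the 15th subject's first scan, with ±7-day windows and 20% of events dated off the grid (assumed). The underlying median at which the PFS limb stops half the time is 4.6 months if event-free subjects are censored at the cutoff, and 5.2 months if censored at their last scan. The unstated convention therefore matters.

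**The case against.** A response-evaluable set is common in a signal-finding pilot, and Section 7 disclaims formal comparisons. Unscheduled scans and the scan at discontinuation bring most early clinical failures to imaging, and entry requires ECOG 0-1 and adequate organ function. The share left unscanned is unknown, and 5-10% is only an assumption. The filter also lowers the chance of stopping a useful regimen. All of this stands and keeps the point minor. It does not remove the direction of the bias: the rule is binding, and the subjects it drops are mostly failures.

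On the grid, the objection is stronger. PFS is defined by documented progression, so scan-dating is part of the endpoint, and the historical 3.5 months may itself be scan-dated. Deaths, unscheduled scans and early-window scans all soften the week-18 effect.

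Three stronger readings are tempting, and the documents do not support them:

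- *The rule is inoperative because the look comes too early for a 6-month median.* At planned accrual, about 8 of the 15 would have at least 26 weeks since enrollment at the look. An unreached median would ordinarily mean not below 6 months, so continue.
- *The grid simply disables the PFS limb.* The limbs are joined by an or, and the grid also spares promising regimens.
- *Response confirmation is missing.* Section 6.1.4.2 asks for it. What is missing is how a response still unconfirmed at the look is counted.

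**Conclusion.** The point holds as a minor one. Followed exactly, the evaluable definition replaces treated subjects who fail unscanned and tilts the look towards continuing. At 10% ORR the chance of passing the response limb goes from 0.18 to 0.20-0.23, if 5-10% of treated subjects are unscanned failures. The exclusion is explicit for the 3-of-15 count. Section 7.2 names no other set for the PFS limb, but applying the filter there is an inference.

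As a secondary note, the 6-month bar gives nearly the same decision as a week-18 (4.1-month) bar for scan-dated events. Under exponential PFS and independent limbs, the either-limb stop falls only from 0.99 to 0.94 at the historical rates, against the illustrative exact-date benchmark. At 20% ORR and a 6-month median it falls from 0.70 to 0.50. The grid thus loses few correct stops and avoids more unwanted ones, so it should be understood rather than called a defect.

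**What to change.** In Section 7.2:

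1. Base both limbs on the first 15 treated subjects. Take the look once each has had a restaging scan, or has died, progressed or discontinued before one.
2. Count death, progression or discontinuation before restaging as non-response. Count death or progression as a PFS event.
3. Name the Kaplan-Meier estimator and the censoring rule for the interim median.
4. Cross-refer the response limb to the confirmation requirement in Section 6.1.4.2, and say how a response not yet confirmed at the look is counted.

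Sections 6.1.4.3 and 6.1.7.3.2 conflict on the off-treatment imaging interval and must be reconciled, since the interval affects when progression is dated. All of this is wording and costs almost nothing.

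The sponsor could instead state the PFS limb as a count failed by the week-27 scan. That is optional and has a real cost: with accrual not paused, about 15 + 1.5 × 6.21 = 24 of 30 would be enrolled at the reading, against 15 + 1.5 × 2.07 = 18 at the first restaging scan.

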1.0 TRIAL SUMMARY

Abbreviated Title	Lenvatinib plus pembrolizumab in patients with immune checkpoint inhibitor naïve metastatic uveal melanoma
Trial Phase	Phase II
Clinical Indication	Treatment of participants with immune checkpoint inhibitor naïve metastatic uveal melanoma
Trial Type	Interventional
Type of control	n/a
Route of administration	Oral and IV
Treatment Groups	Single arm: Lenvatinib 20 mg daily plus pembrolizumab 200 mg IV every 3 weeks.
Number of trial participants	30
Estimated enrollment period	20 months
Estimated duration of trial	48 months (FPFV to LPLV)
Duration of Participation	Subjects will participate in the clinical trial from the time of signing the ICF until the final protocol specified contact. Subjects who discontinue treatment for reasons other than disease progression or treatment related toxicity will have post-treatment follow-up until documented radiographic evidence of disease progression (per iRECIST), initiation of a subsequent anti-cancer therapy, death, pregnancy, withdrawal of consent, lost to follow up or the end of the clinical trial.
Estimated average length of treatment per patient	6 months

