4.0 BACKGROUND & RATIONALE

4.1 Background

Uveal melanoma

Metastatic uveal melanoma is associated with a very poor prognosis with median survival of 6-12 months [1]. Unfortunately, systemic therapy with immune checkpoint inhibitors has demonstrated inadequate efficacy. In a phase II clinical trial with ipilimumab, no objective responses were observed and the median progression free survival (PFS) was 2.8 months [2]. A small phase II clinical trial (17 patients) evaluated the efficacy of pembrolizumab monotherapy. Two out of the 17 patients had an objective response (11.7%) and median PFS was 3.8 months [3]. Treatment with the combination of ipilimumab + nivolumab was evaluated in a phase II clinical trial that showed an objective response rate (ORR) of 18% with median PFS of 5.5 months and median overall survival of 19.1 months [4]. The results of the phase III clinical trial evaluating the bispecific fusion protein Tebentafusp in patients with metastatic uveal melanoma were reported at the 2021 AACR annual meeting. In this clinical trial, patients were randomly assigned (2:1) to either treatment with tebentafusp or investigator choice of therapy (pembrolizumab, ipilimumab or dacarbazine). The authors reported a median overall survival of almost 22 months for tebentafusp compared with 16 months in the investigator choice arm. Tebentafusp resulted in an ORR of 9% [5]. As such, effective therapies for patients with metastatic uveal melanoma represents a significant unmet clinical need.

Pembrolizumab is a potent humanized immunoglobulin G4 (IgG4) monoclonal antibody (mAb) with high specificity of binding to the programmed cell death 1 (PD-1) receptor, thus inhibiting its interaction with programmed cell death ligand 1 (PD-L1) and programmed cell death ligand 2 (PD-

L2). Based on preclinical in vitro data, pembrolizumab has high affinity and potent receptor blocking activity for PD-1. Pembrolizumab has an acceptable preclinical safety profile and is in clinical development as an intravenous (IV) immunotherapy for advanced malignancies. Keytruda[®] (pembrolizumab) is indicated for the treatment of patients across a number of indications because of its mechanism of action to bind the PD-1 receptor on the T cell. For more details on specific indications refer to the Investigator brochure (IB).

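### The printed response-rate power (0.55, 0.78, 0.91) is for a design that always enrols 30 patients, not for the design with the two-part interim stopping rule

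*Combined protocol and SAP*

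**What the plan says.** Section 7.2 gives the setting of the power table as "In this 30 patient pilot study, using a one-sided test with a type I error of 0.05". The quantity is "the power for detecting a difference in the ORR compared with the historical average of 10% ORR with anti-PD-1 monotherapy", and the three entries are 0.55, 0.78 and 0.91 for true rates of 20%, 25% and 30%. The table does not refer to an interim look.

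The next paragraph adds one. Once 15 evaluable subjects have had at least one cycle and restaging imaging, enrollment stops if the ORR is below 20% (3 of 15) "or the median progression free survival is less than 6 months". Because the two limbs are joined by an or, either is sufficient.

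The benchmarks are "median progression free survival of approximately 3.5 months" for PD-1 inhibitors (section 7.2) and, for ipilimumab plus nivolumab, an "objective response rate (ORR) of 18% with median PFS of 5.5 months" (section 4.1). PFS is the primary endpoint (section 3.1) and ORR is secondary (section 3.2). No target median PFS is given, and neither is the stopping probability of either limb, the estimator or minimum follow-up for the interim median, or the power with the interim included. Sections 7.1 and 7.2 also say that formal comparisons are not planned.

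**The concern.** Power is a property of the whole design. A trial stopped at 15 evaluable subjects cannot go on to collect its responses from 30, so a rule that can stop a good regimen must lower the chance of reaching the final response cut-off. Here a regimen with a strong response rate can still be stopped, either by a poor first 15 on response or by a 15-patient median PFS below 6 months.

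Someone using section 7.2 to judge the trial would take 0.91 as the chance of showing a 30% response rate. They could not see how often enrollment would stop early, for an effective or an ineffective regimen.

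**Working it through.** **Inputs.** From section 7.2: n = 30, one-sided alpha 0.05, null ORR 10%, interim at 15, limbs at fewer than 3 of 15 responses and median PFS below 6 months. From section 6.1.4.2: scans every 9 weeks in year 1. From section 1.0: "Estimated enrollment period 20 months", i.e. 30/20 = 1.5 patients per month. Assumed, because the documents are silent: exponential PFS with true median m from 6 to 12 months; final success at 6 or more of 30; all 15 responses known at the interim.

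**Step 1: reproduce the table.** Single-stage normal approximation: Phi[(p1 − 0.10 − 1.645·√(0.10·0.90/30)) / √(p1(1 − p1)/30)].

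At p1 = 0.30: (0.20 − 0.0901)/0.0837 = 1.31, power 0.905. At 25%: 0.776. At 20%: 0.554. All three printed values reproduce with no interim look. The implied critical count is 30 × (0.10 + 0.0901) = 5.70, i.e. 6 or more responses.

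**Step 2: exact single-stage values.** Six or more of 30 has type I error 0.073 and power 0.923 at ORR 30%. Seven or more has type I error 0.026 and power 0.840.

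**Step 3: add the ORR limb.** P(2 or fewer of 15 | 0.30) = 0.127. Power is the sum over x = 3 to 15 of P(x of 15) × P(at least 6 − x of the next 15). At ORR 30% this is 0.843 (0.787 for a cut of 7). At 25% it is 0.690 and at 20% it is 0.467.

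**Step 4: add the PFS limb.** With complete follow-up, the median is below 6 months when at least 8 of 15 have an event before then. The limb is therefore met with probability P(Bin(15, q) ≥ 8).

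- Events dated when they occur: q = 1 − 2^(−6/m).
- Events dated to the scan: scans fall at weeks 9, 18 and 27, about 2.1, 4.1 and 6.2 months, so only progression found by week 18 counts: q = 1 − 2^(−4.14/m), with 18/4.345 = 4.14. This ignores deaths between scans and the ±7-day window. A scan at week 26 falls at 26/4.345 = 5.98 months, so the window can matter.

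Taking response and PFS as independent, full-rule power at ORR 30% is the step 3 value times (1 − probability that the PFS limb is met):

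| True median PFS (months) | PFS limb met: as occurred / scan-dated | Power, 6+ of 30 | Power, 7+ of 30 |
|---|---|---|---|
| 6 | 0.500 / 0.169 | 0.421 / 0.700 | 0.393 / 0.654 |
| 8 | 0.226 / 0.052 | 0.652 / 0.800 | 0.609 / 0.746 |
| 10 | 0.098 / 0.017 | 0.760 / 0.828 | 0.710 / 0.774 |
| 12 | 0.044 / 0.006 | 0.806 / 0.838 | 0.753 / 0.782 |

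**Step 5: sensitivity.** If responders never progress before 6 months (events dated as they occur, cut of 6), power is 0.48, 0.70, 0.79 and 0.82 at 6, 8, 10 and 12 months, inside the ranges above. If the rule is applied at the 15th subject's first scan with a Kaplan-Meier median, the limb is met with probability about 0.25 at 8 months and 0.07 at 12 months. Power is then 0.843 × 0.75 = 0.63 and 0.843 × 0.93 = 0.78 under independence, about 2 points below the lower ends.

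**Step 6: the null side.** At ORR 10% and median 3.5 months, the ORR limb stops enrollment with probability 0.82. The PFS limb does so with probability 0.95 (0.68 scan-dated). The ORR limb also lowers the type I error of the 6-response cut from 0.073 to 0.054.

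**The case against.** **The plan disclaims formal comparisons.** This is a signal-finding pilot and no planned claim rests on 0.91. That limits the consequence. It does not make 0.91 the power of the written design, because the plan chose to print power for a stated one-sided test and its stopping rule is worded as binding.

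**A futility rule is meant to cost some power.** This stands. Step 6 shows that the rule works well against an ineffective regimen. The fault is that its effect is not reported.

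**A 6-month bar suits this trial.** A reader might infer that 6 months is too high for a futility level, since it exceeds the historical 3.5 months and every median PFS cited in section 4.1. The documents do not support calling that an error. PFS is primary, and the stated hypothesis is to improve on therapies that include ipilimumab plus nivolumab at 5.5 months. A bar just above that is a defensible choice.

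**Response overriding PFS.** A reader might also infer that a clear response signal should cancel the PFS limb. That would let a secondary endpoint override the primary one. It is a design choice for the sponsor, and nothing in the documents settles it.

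**Conclusion.** The point holds as a reporting defect. The printed 0.55, 0.78 and 0.91 are single-stage figures and do not belong to the design in section 7.2. In every scenario computed at ORR 30% with a true median of 6 to 12 months, full-rule power is below 0.91.

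No single replacement value can be given. The ranges of roughly 0.42–0.70, 0.65–0.80 and 0.80–0.84 at true medians of 6, 8 and 12 months rest on exponential PFS, a success cut of 6 or more, and two ways of dating events. Immature follow-up could take the lower ends down by about 2 points.

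Two stronger readings should be resisted. The PFS limb is not the sole cause: the ORR limb alone takes exact power from 0.92 to 0.84, and at a 12-month median the PFS limb adds little. Nor does the rule end the trial: it stops enrollment, and section 7.2 does not stop treatment or follow-up of patients already enrolled.

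**What to change.** In section 7.2:

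1. Label the current table as single-stage power for 30 patients, calculated without the interim rule.
2. Beside it, give the probability of stopping enrollment and the power of the complete rule, both limbs included, for true ORR 10%, 20%, 25% and 30% crossed with true median PFS 3.5, 6, 8, 10 and 12 months. The 10% row gives the type I error.
3. State the assumptions behind that grid: the final success cut-off (6 or more of 30 has an exact type I error of 0.073 before any interim; 7 or more has 0.026), when the interim is done and with what follow-up, how the interim median is estimated, and how PFS events are dated.

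The stopping rule itself need not change. The cost is a short simulation and a wording change. The downside is that the stated power becomes less favourable.
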